5.3. REMOVAL OF SUBJECTS FROM STUDY TREATMENT AND/OR STUDY AS A WHOLE

Subjects can be taken off the study treatment and/or study as a whole at any time at their own request, or they may be withdrawn at the discretion of the investigator for safety, behavioral or administrative reasons. In the case that a subject is removed from the study due to safety reasons, the FDA and other global regulatory authority will be notified. The reason(s) for discontinuation must be clearly documented on the appropriate eCRF and may include:

- Subject voluntarily withdraws from treatment (follow-up permitted)
- Subject withdraws consent (no follow-up permitted)
- Subject is unable to comply with protocol requirements

CONFIDENTIAL Page 61 of 108

- Subject experiences unacceptable toxicity
- Treating physician determines that continuation on the study would not be in the subject's best interest
- Subject becomes pregnant
- Subject becomes lost to follow-up (LTF)
- Subject will be withdrawn from the study if 2 consecutive injections of study drug are missed
- Subject manifesting Grade 4 or Grade 3 toxicity attributable to the Leronlimab (PRO 140)

If a subject fails to return for the scheduled study visit or is discontinued from the study, an attempt will be made to determine the reason(s). If the subject is unreachable by telephone, a registered letter will be sent to the subject requesting that he/she contact the clinic.

All patients with an ongoing SAE or AE attributable (definitely, probably, or possibly related) to the study treatment at the Post-Study (Follow-up) Visit (scheduled or premature) must be followed until the event is resolved (with or without sequelae) or deemed stable.

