Subjects who meet the eligibility criteria will have completed the following evaluations and assessments at V2 prior to treatment: review of any changes in medical and medication history, physical examination, vital signs, clinical status – ordinal scale assessment, PaO2/FiO2 measurement, pulse oxygen saturation (SpO2), positive end-expiratory pressure (PEEP) (for intubated subjects), sequential Organ Failure Assessment (SOFA) score, National Early Warning Score 2 (NEWS2) assessment, nasopharyngeal swab sample collection, baseline assessment for the requirement of: mechanical ventilation, non-invasive ventilation, supplemental oxygen, vasopressors use, renal replacement therapy, ICU admission and hospital stay, assessment for any new infections, blood sample collection for CD3+, CD4+ and CD8+ T cell count, CCR5 receptor occupancy for Treg and macrophages, serum cytokine and chemokine levels, and CCR5 gene polymorphisms. After administration of leronlimab subjects will be assessed for vital sign, adverse event and concomitant medications. If Visit 2 (V2) takes place on the same day as the Screening

CONFIDENTIAL Page 48 of 108

Visit (V1), scheduled assessments performed under screening (V1) do not need to be repeated at V2.

Table 4-1: Treatment Groups

Study Drug	Dosage Form	IP concentration	Dosing Frequency and Amount	Route of Administration
PRO 140 (700 mg)	Parenteral solution	175 mg/mL	2 injections of PRO 140 (2 X 2 mL/inj.) per week on opposite sides of abdomen	SC injection
Placebo	Parenteral solution	0 mg/mL	2 injections of placebo (2 X 2 mL/inj.) per week on opposite sides of abdomen	SC injection

At V2, subjects will be randomized to receive leronlimab (PRO 140) or placebo which will be administered subcutaneously weekly at Visit 2 (Day 0) and Visit 4 (Day 7) by a qualified medical professional at clinic. If the subject is discharged from the hospital prior to Visit 7 (Day 42), the visit can be completed at the subject's home.

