5.4. DATA COLLECTED FROM WITHDRAWN SUBJECTS

Every attempt should be made to collect follow-up information. The reason for withdrawal from the study will be recorded in the source documents and on the appropriate page of the CRF.

Before a subject is identified as lost-to-follow up, the site should make all reasonable efforts to contact the subject. These attempts must be documented and should include at a minimum one phone call and one certified letter.

In the event that a subject is withdrawn from the study at any time due to an adverse event or SAE, the procedures stated in Section 9 (Safety) must be followed.

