6. STUDY TREATMENT

Leronlimab (PRO 140) or placebo will be administered subcutaneously (SC) at a weekly as follows:

Table 6-1: Treatment Administration Summary

Study Drug	Dose	Route	Schedule
Leronlimab (PRO 140)	$700~\mathrm{mg}$	SC	Weekly (2 doses)
Placebo	$0~\mathrm{mg}$	SC	Weekly (2 doses)

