6.1. LERONLIMAB (PRO 140)

Leronlimab (PRO 140) is a humanized IgG4,κ monoclonal antibody (mAb) to the chemokine receptor CCR5. Leronlimab (PRO 140) is provided at a concentration of 175 mg/mL and is intended for SC route of administration.

Leronlimab (PRO 140) kit will contain two vials. Each vial of the Leronlimab (PRO 140) product contains ~2.4 mL antibody at 175mg/mL in a buffer containing 5 mM L-histidine, 15.0 mM glycine, 95 mM sodium chloride, 0.3% (w/v) sorbitol, 0.005% (w/v) polysorbate 20 (Tween 20[®]), and sterile water for injection, at pH of 5.5. For subjects assigned to Leronlimab (PRO 140) arm, one kit will be assigned per treatment visit.

Note: 2 mL will be drawn from 2.4 mL solution filled vial. Remaining 0.4 mL medication will be discarded appropriately from each vial.

Isotonic 0.9% Sodium Chloride Injection, USP will be used as Placebo.

A dose of 700 mg of Leronlimab (PRO 140) (175 mg/mL) or placebo will be delivered as two injections of 2 mL each and administered subcutaneously on opposite sides of the abdomen.

Table 6-2: Investigational Product - Leronlimab (PRO 140)

IP Dosage	Dosage Form	IP concentration	Dosing Frequency and Amount	Route of Administration
PRO 140 700 mg	Parenteral solution	175 mg/mL	2 injections of PRO 140 (2 mL/inj.) per week on opposite sides of abdomen for two weeks	SC injection
Placebo	Parenteral solution	0 mg/mL	2 injections of placebo (2 X 2 mL/inj.) per week on opposite sides of abdomen for two weeks	SC injection

Note: Patients with low body fat percentages may find subcutaneous injections uncomfortable. In such cases, leronlimab (PRO 140) 700 mg can be injected as four 175mg/ml injections and/or subcutaneous injections can be placed at different areas other than abdomen as per discretion of the Investigator.

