11.4.1. Major Protocol Deviation or Violation

[figure not shown]
A major protocol deviation or violation is a deviation from the IRB approved protocol that may affect the subject's rights, safety, or well being and/or the completeness, accuracy and reliability of the study data. Examples of this include:

- Failure to obtain informed consent prior to initiation of study-related procedures
- A research subject does not meet the protocol's eligibility criteria but was enrolled without prior approval from the sponsor.
- A research subject received the wrong treatment or incorrect dose.
- A research subject met withdrawal criteria during the study but was not withdrawn.
- A research subject received a prohibited concomitant medication.
- Failure to treat research subjects per protocol procedures that specifically relate to primary efficacy outcomes.
- Changing the protocol without prior sponsor and IRB approval.
- Multiple minor violations of the same nature after multiple warnings.

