### 7.3 PP Population

The **Per Protocol (PP) population** is defined as the set of subjects who meet the ITT Population requirements and are not associated with any major protocol violations per ICH definition including:

- · Informed consent not properly attained
- Did not meet inclusion/ exclusion criteria but entered into study

Note: Subjects who have confirmed COVID-19 diagnosis but results not available within 5 days of screening will not be considered major protocol deviation/violation.

- Developed withdrawal criteria during the study, but not withdrawn
- Study drug dosing deviation

Note: Subjects who do not receive two doses of study treatment (except in case of mortality within 7 days of treatment initiation) will be considered major protocol deviation/violation and will be excluded from the PP population.

Received excluded concomitant medication

This population will be identified programmatically before the database lock. This population will be used as the supportive analysis population for analysis of the primary and secondary efficacy endpoints.

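### Protocol 5.3 removes subjects from the study for missed injections, and nothing requires their Day 28 vital status, so primary-endpoint data may be lost

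*Protocol*

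**What the plan says.** Protocol 5.3 lists reasons for removal from treatment or from the study. Most items are possible reasons to be documented, but one is mandatory and concerns the study itself: "Subject will be withdrawn from the study if 2 consecutive injections of study drug are missed". The same list has a treatment-only exit with follow-up permitted. It bars follow-up only when consent is withdrawn.

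The dosing text counts injections singly. Protocol 6.1 says a 700 mg dose "will be delivered as two injections of 2 mL each and administered subcutaneously on opposite sides of the abdomen", and Table 4-1 gives "2 injections of PRO 140 (2 X 2 mL/inj.) per week on opposite sides of abdomen". Table 6-1 sets two weekly doses. For some subjects Protocol 6.1 adds that "leronlimab (PRO 140) 700 mg can be injected as four 175mg/ml injections". The objective in Protocol section 2, however, describes the weekly administration in the singular, as one injection.

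Non-withdrawal is penalised. Protocol 11.4.1 gives as an example of a major violation: "A research subject met withdrawal criteria during the study but was not withdrawn". SAP 7.3 excludes from the per-protocol set anyone who "Developed withdrawal criteria during the study, but not withdrawn". As a separate item, SAP 7.3 treats receipt of fewer than two doses as a major dosing deviation (deaths within 7 days excepted) and does not mention study withdrawal.

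On follow-up, Protocol 5.4 says: "Every attempt should be made to collect follow-up information". Protocol 9.5 requires subjects with an SAE, including discontinued ones, to be followed to resolution, stabilisation or death. The primary endpoint is all-cause mortality at Day 28. The primary population is ITT in the protocol and mITT (at least one dose) in the SAP. Missing efficacy data are multiply imputed (Protocol 8.9.3, SAP 8.3).

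**The concern.** Death by Day 28 can be ascertained whatever number of doses a subject received. A subject who had the Day 0 dose and missed Day 7 belongs in the primary analysis under either document. A non-adherence rule that ends study participation works against that analysis, because it removes the scheduled Day 28 and Day 42 contacts at which vital status is recorded.

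The loss need not be random. A Day 7 dose may be missed because of transfer, deterioration or toxicity, and Protocol 6.1.5 itself directs withholding or discontinuation for some events attributed to leronlimab. Missingness could therefore depend on outcome or on arm. The only covariate the plan names for the imputation model is the stratification factor; the reason for withdrawal is not mentioned. Imputation would then stand in for a fact that a telephone call or a records check could often supply.

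**Working it through.** **1. When the rule applies.**
- Injection counted singly: 1 weekly dose = 2 injections, so missing Day 7 alone = 2 consecutive missed injections and study withdrawal. With the four-injection option, 2 missed injections are 2/4 = half of one dose.
- Injection meaning the weekly administration: 2 consecutive misses = both doses, so only never-dosed subjects are caught. They are in ITT but outside the SAP's mITT.

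The dosing tables favour the first reading. The objective, and the separate treatment of under-dosing in SAP 7.3, leave room for the second.

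**2. What is secured after withdrawal.** Protocol 5.4 is a general best-efforts clause that names neither Day 28 nor vital status. Protocol 9.5 is firm but reaches only subjects with an SAE. Protocol 5.3 adds follow-up of ongoing treatment-attributable events. A withdrawn subject without such an event is covered by 5.4 alone.

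**3. The plan's own sample size.** Inputs (Protocol 8.3): 45% vs 30%, 2:1 allocation, two-sided 0.05, 80% power, 5% dropout. With unpooled variance, placebo n = (1.960 + 0.842)² × (0.45×0.55 + 0.30×0.70/2) / 0.15² = 122.97, rounded up to 123. The total is 3 × 123 = 369, as stated. Then 369/0.95 = 388.4, or 389 against the 390 stated. The figure reproduces, so nothing here rests on a sample-size error. The allowance is 390 − 369 = 21 subjects for all causes of loss.

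**4. Power if Day 28 status is lost.** Loss rates are assumed. Pooled-variance z-test at the design rates:

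| Loss per arm | Power |
|---|---|
| 0% | 82.9% |
| 5% | 81.0% |
| 10% | 78.9% |
| 15% | 76.7% |

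**5. Bounds on the risk difference** (leronlimab minus placebo). With a fraction m unknown per arm and 30% vs 45% among those observed, the bounds are −0.15(1 − m) ± m.
- m = 5%: −19.3 to −9.3 points
- m = 10%: −23.5 to −3.5 points
- m = 15%: −27.8 to +2.3 points (the sign is no longer fixed)

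**6. Illustrative p-values.** Pooled z = (p₁ − p₂)/√[p(1 − p)(1/n₁ + 1/n₂)]. Assume 5% unknown: 13 of 260 and 7 of 130, leaving 247 and 123. Design rates give 0.30 × 247 ≈ 74 and 0.45 × 123 ≈ 55 deaths.

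| Assumption about the 20 missing | Deaths | p |
|---|---|---|
| Observed only | 74/247 vs 55/123 | 0.005 |
| No leronlimab deaths, all 7 placebo die | 74/260 vs 62/130 | 0.0002 |
| All 13 leronlimab die, no placebo deaths | 87/260 vs 55/130 | 0.087 |
| Design rates reversed (6/13 vs 2/7) | 80/260 vs 57/130 | 0.011 |

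**The case against.** The other side has four fair points.

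- **Meaning of the term.** Two syringes given at one visit are not naturally two consecutive injections, and the four-injection option makes the literal reading odd, since half a dose would trigger withdrawal. A reader might infer that anyone who misses Day 7 is certainly withdrawn. The documents do not settle that, because they use the word both ways. This point stands, and it makes the undefined term part of the defect.
- **No conflict between 5.4 and 11.4.1.** A reader might infer that a site cannot keep following a subject without committing a violation. That is not so. The violation is failing to withdraw, and a site can withdraw the subject and still collect vital status. The per-protocol exclusion also touches only a supportive analysis; the subject stays in ITT, and in mITT if dosed.
- **Existing safeguards.** Protocol 9.5 covers much of the deterioration and toxicity route. Home visits allow dosing after discharge, and the follow-up visits can be by telephone or video. This narrows the gap but does not close it, because none of it requires Day 28 status for every withdrawn subject.
- **Size.** A reader might take the p-value range as the effect of this rule. It is not. The 5% is the overall dropout allowance, here assigned wholly to missing Day 28 status with none recovered, and the upper bound needs every missing leronlimab subject to die and every missing placebo subject to survive. The milder reversal stays at p = 0.011.

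**Conclusion.** The point holds as a gap in the plan. A mandatory rule ends study participation for missed injections, its trigger is undefined, and the follow-up provisions do not guarantee the primary endpoint for those withdrawn. Vital status may be lost and imputed, possibly informatively; the documents do not show that it will be.

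The size is unknown because no missed-dose rate is given. The figures show sensitivity to missing Day 28 status under assumed loss rates. At 5% loss and the design rates, only an extreme pattern moves the result past 0.05. Power falls below 80% at about 10% loss, and the sign of the difference is no longer fixed by the bounds at 15%. The correction is worth making because it is cheap and protects the primary endpoint.

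**What to change.** 1. Define injection in Protocol 5.3, and reconcile Protocol 5.3, 5.4, 6.1.5 and 11.4.1 with SAP 7.3.
2. Separate stopping study treatment from leaving the study. Subjects who miss doses remain in follow-up for Day 28 and Day 42 vital status unless consent to follow-up is withdrawn.
3. State that continued follow-up after missed doses is not an instance of the violation for subjects who met withdrawal criteria but were kept in the study.
4. Before database lock, retrieve vital status and date of death for every randomised subject recorded as withdrawn, where consent allows, and use it in the primary analysis (mITT in the SAP, ITT in the protocol). This step is useful even with randomised enrolment complete.

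The cost is wording changes in the two documents and a records or telephone check; the planned 5% dropout implies about 20 subjects. No dose or treatment-stopping rule is proposed.

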5.4. DATA COLLECTED FROM WITHDRAWN SUBJECTS

Every attempt should be made to collect follow-up information. The reason for withdrawal from the study will be recorded in the source documents and on the appropriate page of the CRF.

Before a subject is identified as lost-to-follow up, the site should make all reasonable efforts to contact the subject. These attempts must be documented and should include at a minimum one phone call and one certified letter.

In the event that a subject is withdrawn from the study at any time due to an adverse event or SAE, the procedures stated in Section 9 (Safety) must be followed.

5.5. SCREEN FAILURES

A subject who signed a consent form, but did not meet the inclusion/exclusion criteria is classified as a screen failure. Subject number, demographics and reason for screen failure will be recorded.

In the event that a subject initially fails to meet inclusion/exclusion criteria and is later reconsidered for participation, the subject will be re-consented and assigned a new screening number at the time of re-screening. Subjects who fail their first screening attempt may be re-screened again (i.e., up to two screenings) and may be enrolled if they are found to meet all inclusion and no exclusion criteria at the subsequent screening visit.

CONFIDENTIAL Page 62 of 108

6. STUDY TREATMENT

Leronlimab (PRO 140) or placebo will be administered subcutaneously (SC) at a weekly as follows:

Table 6-1: Treatment Administration Summary

Study Drug	Dose	Route	Schedule
Leronlimab (PRO 140)	$700~\mathrm{mg}$	SC	Weekly (2 doses)
Placebo	$0~\mathrm{mg}$	SC	Weekly (2 doses)

6.1. LERONLIMAB (PRO 140)

Leronlimab (PRO 140) is a humanized IgG4,κ monoclonal antibody (mAb) to the chemokine receptor CCR5. Leronlimab (PRO 140) is provided at a concentration of 175 mg/mL and is intended for SC route of administration.

Leronlimab (PRO 140) kit will contain two vials. Each vial of the Leronlimab (PRO 140) product contains ~2.4 mL antibody at 175mg/mL in a buffer containing 5 mM L-histidine, 15.0 mM glycine, 95 mM sodium chloride, 0.3% (w/v) sorbitol, 0.005% (w/v) polysorbate 20 (Tween 20[®]), and sterile water for injection, at pH of 5.5. For subjects assigned to Leronlimab (PRO 140) arm, one kit will be assigned per treatment visit.

Note: 2 mL will be drawn from 2.4 mL solution filled vial. Remaining 0.4 mL medication will be discarded appropriately from each vial.

Isotonic 0.9% Sodium Chloride Injection, USP will be used as Placebo.

A dose of 700 mg of Leronlimab (PRO 140) (175 mg/mL) or placebo will be delivered as two injections of 2 mL each and administered subcutaneously on opposite sides of the abdomen.

Table 6-2: Investigational Product - Leronlimab (PRO 140)

IP Dosage	Dosage Form	IP concentration	Dosing Frequency and Amount	Route of Administration
PRO 140 700 mg	Parenteral solution	175 mg/mL	2 injections of PRO 140 (2 mL/inj.) per week on opposite sides of abdomen for two weeks	SC injection
Placebo	Parenteral solution	0 mg/mL	2 injections of placebo (2 X 2 mL/inj.) per week on opposite sides of abdomen for two weeks	SC injection

Note: Patients with low body fat percentages may find subcutaneous injections uncomfortable. In such cases, leronlimab (PRO 140) 700 mg can be injected as four 175mg/ml injections and/or subcutaneous injections can be placed at different areas other than abdomen as per discretion of the Investigator.

6.1.1. Leronlimab (PRO 140) - Packaging and Labeling

CONFIDENTIAL Page 63 of 108

Study drug will be prepared by Ajinomoto Althea, Inc. and will be packaged, labeled, and shipped by Sherpa Clinical Packaging, LLC.

The contents of each vial are described in Section 6.1. Leronlimab (PRO 140) kits will be labeled with information such as: study protocol #; fill volume; concentration; storage condition; a "use as per study protocol" statement; a cautionary statement; sponsor's name and address; and the kit number.

Below are representative samples of the Investigational Product, finished drug product (FDP) individual vial (Figure 6-1), syringe label (Figure 6-2), and kit labels (Figure 6-3) designated for use in this clinical protocol. Each kit contains two labeled vials and two syringe labels.

Figure 6-1: Investigational Product - Vial Label

Protocol: CD12_COVID-19 Kit No. xxx	Protocol: CD12_COVID-19 Kit No. xxx
Subject No	Subject No
Single use 3 mL vial contains 2.4 mL of PRO 140 (175 mg/mL) solution for subcutaneous injection	Single use 3 mL vial contains 2.4 mL of PRO 140 (175 mg/mL) solution for subcutaneous injection
Store at 2°C to 8°C (36°F to 46°F)	Store at 2°C to 8°C (36°F to 46°F)
USE AS PER STUDY PROTOCOL	USE AS PER STUDY PROTOCOL
Caution: New Drug – Limited by Federal (or United States) Law to Investigational Use	Caution: New Drug – Limited by Federal (or United States) Law to Investigational Use
CytoDyn Inc., Vancouver, WA, USA	CytoDyn Inc., Vancouver, WA, USA

Figure 6-2: Investigational Product - Syringe Label

Protocol: CD12_COVID-19

This syringe contains 2 mL PRO 140 (175 mg/mL) or placebo solution for subcutaneous injection

USE AS PER STUDY PROTOCOL

[figure not shown]
Caution: New Drug – Limited by Federal (or United States) Law to Investigational Use

CytoDyn Inc., Vancouver, WA, USA

Figure 6-3: Investigational Product - Kit Label

Protocol: CD12_COVID-19	Kit No. xxx

CONFIDENTIAL Page 64 of 108

ite No Subject No		
This kit contains 2 single-use vials		
ach 3 mL vial contains 2.4 mL of PRO 140 (175 mg/mL) solution for abcutaneous injection		
tore at 2°C to 8°C (36°F to 46°F)		
ISE AS PER STUDY PROTOCOL		
Caution: New Drug – Limited by Federal (or United States) Law to Investigational Use		
SytoDyn Inc., Vancouver, WA, USA		

The pharmacy manual provides the criteria regarding vial acceptance or rejection, as well as instructions for the preparation of the IP syringes to be used to administer drug.

6.1.2. Leronlimab (PRO 140) - Storage and Handling

Study drug will be shipped at 2°C to 8°C (refrigerated [36°F to 46°F]) to the investigator's site. Upon receipt at the site, the responsible site staff or pharmacist should verify the integrity of the vials. Study drug should be stored at 2°C to 8°C (refrigerated [36°F to 46°F]). The contents of the vial should appear as a clear to opalescent, colorless to yellow solution; fine translucent particles may be present. This is normal.

The investigator must maintain an accurate record of the shipment, storage, and dispensing of the study drug in a drug accountability log. An accurate record including the date and amount of study drug dispensed to each subject must be available for inspection at any time. A study CRA assigned to monitor the investigational site will review these documents once study drug has been received by the investigational site. Study drug will be accounted for on an ongoing basis during the study.

